## **5.6 Rescue Medications & Supportive Care**

No rescue or supportive medications are specified to be used in this trial.

### **5.6.1 Supportive Care Guidelines**

Subjects should receive appropriate supportive care measures as deemed necessary by the treating investigator. Suggested supportive care measures for the management of AEs with potential immunologic etiology are outlined along with the dose modification guidelines in Section 5.2.1.2.1, [Table 4]. Where appropriate, these guidelines include the use of oral or IV treatment with corticosteroids, as well as additional anti-inflammatory agents if symptoms do not improve with administration of corticosteroids. Note that several courses of steroid tapering may be necessary as symptoms may worsen when the steroid dose is decreased. For each disorder, attempts should be made to rule out other causes such as metastatic disease or bacterial or viral infection, which might require additional supportive care. The treatment guidelines are intended to be applied when the investigator determines the events to be related to pembrolizumab.

Note: If after evaluation of the event, it is determined not to be related to pembrolizumab, the investigator does not need to follow the treatment guidance. It may be necessary to perform conditional procedures such as bronchoscopy, endoscopy, or skin photography as part of evaluation of the event.

Instructions regarding supportive care needed with the chemotherapeutic agents administered in this study can be found in the local product label for each agent. Infusion reactions and injection site reactions will be managed by the investigator according to local product labeling.

## **5.7 Diet/Activity/Other Considerations**

### **5.7.1 Diet**

Subjects should maintain a normal diet unless modifications are required to manage an AE such as diarrhea, nausea, or vomiting.

### **5.7.2 Contraception**

Pembrolizumab may have adverse effects on a fetus in utero. Furthermore, it is not known if pembrolizumab has transient adverse effects on the composition of sperm.

For this trial, male subjects will be considered to be of non-reproductive potential if they have azoospermia (whether due to having had a vasectomy or due to an underlying medical condition).

Chemotherapy can cause fetal harm if administered to pregnant women. Therefore, non-pregnant, non-breastfeeding women may be enrolled if they are considered of non-reproductive potential.

Female subjects will be considered of non-reproductive potential if they meet one of the following criteria:

- She is postmenopausal, defined as at least 12 months with no menses without an alternative medical cause. In women <45 years of age who are not using hormonal contraception or hormonal replacement therapy, a high follicle-stimulating hormone (FSH) level in the postmenopausal range may be used to confirm a post-menopausal state. In the absence of 12 months of amenorrhea, a single FSH measurement is insufficient.
- She had a hysterectomy and/or bilateral oophorectomy, bilateral salpingectomy, or bilateral tubal ligation/occlusion at least 6 weeks prior to screening.
- She has a congenital or an acquired condition that prevents childbearing.

Female and male subjects of reproductive potential must agree to avoid becoming pregnant or impregnating a partner, respectively, while receiving trial drug and for 120 days after the last dose of pembrolizumab and for 180 days after the last dose of chemotherapy by complying with one of the following:

- Practice abstinence from heterosexual activity.
- Abstinence (relative to heterosexual activity) can be used as the sole method of contraception if it is consistently employed as the subject's preferred and usual lifestyle and if considered acceptable by local regulatory agencies and Ethics Review Committees (ERCs)/Institutional Review Boards (IRBs). Periodic abstinence (eg, calendar, ovulation, symptothermal, post-ovulation methods) and withdrawal are not acceptable methods of contraception.
- Use (or have their partner use) acceptable contraception during heterosexual activity.

Acceptable methods of contraception are‡:

- Single method (one of the following is acceptable):
  - Intrauterine device (IUD)
  - Vasectomy of a female subject's male partner
  - Contraceptive rod implanted into the skin
- Combination method (requires use of 2 of the following):
  - Diaphragm with spermicide (cannot be used in conjunction with cervical cap/spermicide)
  - Cervical cap with spermicide (nulliparous women only)
  - Contraceptive sponge (nulliparous women only)
  - Male condom or female condom (cannot be used together)
  - Hormonal contraceptive: oral contraceptive pill (estrogen/progestin pill or progestin-only pill), contraceptive skin patch, vaginal contraceptive ring, or subcutaneous contraceptive injection

‡If a contraceptive method listed above is restricted by local regulations/guidelines, then it does not qualify as an acceptable method of contraception for subjects participating at sites in this country/region.

Subjects should be informed that taking the trial medication may involve unknown risks to the fetus (unborn baby) if pregnancy were to occur during the trial. In order to participate in

the trial, subjects of childbearing potential must adhere to the contraception requirement (described above) from the day of trial medication initiation (or 14 days prior to the initiation of trial medication for oral contraception) throughout the trial period up to 120 days after the last dose of pembrolizumab and up to 180 days after last dose of chemotherapeutic agents. If there is any question that a subject of childbearing potential will not reliably comply with the requirements for contraception, that subject should not be entered into the trial.

If a female subject inadvertently becomes pregnant while on treatment in this study, the subject will immediately be removed from the study. The site will contact the subject at least monthly and document the subject's status until the pregnancy has been completed or terminated. The outcome of the pregnancy will be reported to the Sponsor without delay and within 24 hours if the outcome is an SAE (eg, death, abortion, congenital anomaly, or other disabling or life-threatening complication to the mother or newborn). The study investigator will make every effort to obtain permission to follow the outcome of the pregnancy and report the condition of the fetus or newborn to the Sponsor. If a male subject impregnates his female partner, the study personnel at the site must be informed immediately and the pregnancy reported to the Sponsor and followed as described above and in Section 7.2.

### **5.7.3 Use in Nursing Women**

It is unknown whether pembrolizumab is excreted in human milk. As many drugs are excreted in human milk, and because of the potential for serious adverse reactions in the nursing infant, subjects who are breast-feeding are not eligible for enrollment.

## **5.8 Subject Withdrawal/Discontinuation Criteria**

### **5.8.1 Discontinuation of Treatment**

Discontinuation of trial treatment does not represent withdrawal from the trial.

As certain data on clinical events beyond treatment discontinuation may be/are important to the study, they must be collected through the subject's last scheduled follow-up, even if the subject has discontinued trial treatment. Therefore, all subjects who discontinue trial treatment prior to completion of the treatment period will still continue to participate in the trial as specified in Section 6.0 and Section 7.1.5.7.

Subjects may discontinue treatment at any time for any reason or be dropped from trial treatment at the discretion of the investigator should any untoward effect occur. In addition, a subject may be discontinued from trial treatment by the investigator or the Sponsor if treatment is inappropriate, the trial plan is violated, or for administrative and/or other safety reasons. Specific details regarding procedures to be performed at treatment discontinuation are provided in Section 7.1.4 – Other Procedures.

A subject must be discontinued from trial treatment but continue to be monitored in the trial for any of the following reasons:

- The subject or subject's legally acceptable representative requests to discontinue trial treatment.
- Confirmed radiographic disease progression, as outlined in Section 7.1.5 (exception if the Sponsor approves treatment continuation)

Note: Subjects with new asymptomatic brain metastasis may be eligible to continue study treatment at the discretion of the investigator after consultation with the Sponsor. Section 7.1.2.7.6 provides details regarding eligibility requirements and subsequent radiographic assessments.

- Unacceptable AEs, as described in Section 7.2
- Any progression or recurrence of any malignancy, or any occurrence of another malignancy that requires active treatment
- Intercurrent illness other than another malignancy as noted above that prevents further administration of treatment
- Recurrent Grade 2 pneumonitis
- Recurrent Grade 3 diarrhea
- A confirmed positive serum pregnancy test
- Noncompliance with trial treatment or procedure requirements
- Investigator's decision to withdraw the subject
- Completion of 35 cycles of trial treatments (approximately 2 years)

Note: The number of treatments is calculated starting with the first dose. Subjects who stop trial treatment after receiving 35 doses of pembrolizumab or saline placebo may be eligible for the Second Course Phase (retreatment) if they progress after stopping trial treatment, provided they meet the requirements detailed in Section 7.1.5.5. Only subjects who were assigned to the pembrolizumab arm may be retreated in the Second Course Phase for up to an additional 17 cycles (approximately 1 year).

For subjects who are discontinued from trial treatment but continue to be monitored in the trial, all visits and procedures, as outlined in the trial flowchart, should be completed.

Discontinuation from trial treatment is "permanent." Once a subject is discontinued, he/she shall not be allowed to restart treatment.

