**1.0 TRIAL SUMMARY**

Abbreviated Title	Phase 3 trial of first line etoposide/platinum (EP) with or without pembrolizumab in ES-SCLC (KEYNOTE-604)
Sponsor Product Identifiers	MK-3475 Pembrolizumab
Trial Phase	III
Clinical Indication	First-line treatment of extensive stage small cell lung cancer (ES-SCLC) in combination with standard of care (SOC) chemotherapy
Trial Type	Interventional
Type of control	Placebo
Route of administration	Intravenous (IV)
Trial Blinding	Double-blind
Treatment Groups	
Arm 1: Pembrolizumab + EP:  Pembrolizumab 200 mg IV every 3 weeks (Q3W) on Day 1  Etoposide 100 mg/m^2 IV Q3W on Days 1, 2, and 3  Platinum, investigator's choice  Carboplatin titrated to an area under the plasma drug concentration-time curve (AUC) of 5 IV Q3W on Day 1  OR  Cisplatin 75 mg/m^2 IV Q3W on Day 1
 
Arm 2: Placebo + EP:  Placebo IV Q3W on Day 1  Etoposide 100 mg/m^2 IV Q3W on Days 1, 2, and 3  Platinum, investigator's choice  Carboplatin titrated to an AUC of 5 IV Q3W on Day 1  OR  Cisplatin 75 mg/m^2 IV Q3W on Day 1

Number of trial subjects	Approximately 430 subjects will be enrolled.
Estimated duration of trial	The Sponsor estimates that the trial will require approximately 4.5 years from the time the first subject signs the informed consent until the last subject's last study-related phone call or visit.
Duration of Participation	
Each subject will participate in the trial from the time the subject signs the informed consent form through the final protocol-specified contact.
 
After a screening phase of up to 28 days, each subject will be randomized to receive trial treatment (pembrolizumab + EP or placebo + EP). The SOC treatment component (EP) will be given for the first 4 cycles with pembrolizumab or placebo, after which partial and complete responders may receive prophylactic cranial irradiation at the discretion of the investigator. Treatment with pembrolizumab or placebo will continue until a total of 35 cycles of treatment have been administered or until one of the treatment discontinuation criteria occurs: confirmed disease progression, unacceptable adverse event(s) (AEs), intercurrent illness,

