### 5.2.1.2.1 Pembrolizumab

Adverse events (both non-serious and serious) associated with pembrolizumab exposure may have an immunologic etiology. These immune-related AEs (irAEs) may occur shortly after the first dose or several months after the last dose of treatment and may affect more than one body system simultaneously. Therefore, early recognition and initiation of treatment is

critical to reduce complications. Based on existing clinical trial data, most irAEs were reversible and could be managed with interruptions of pembrolizumab, administration of corticosteroids, and/or other supportive care. For suspected irAEs, ensure adequate evaluation to confirm etiology or exclude other causes. Additional procedures or tests such as bronchoscopy, endoscopy, or skin biopsy may be included as part of the evaluation. Based on the severity of the irAE, withhold or permanently discontinue pembrolizumab and administer corticosteroids. Dose modification and toxicity management guidelines for irAEs associated with pembrolizumab are provided in [Table 4](#).

Table 4 Dose Modification and Toxicity Management Guidelines for Immune-Related AEs Associated With Pembrolizumab

General instructions:				
1. Corticosteroid taper should be initiated upon AE improving to Grade 1 or less and continue to taper over at least 4 weeks. 2. For situations where pembrolizumab has been withheld, pembrolizumab can be resumed after AE has been reduced to Grade 1 or 0 and corticosteroid has been tapered. Pembrolizumab should be permanently discontinued if AE does not resolve within 12 weeks of last dose or corticosteroids cannot be reduced to $\leq 10$ mg prednisone or equivalent per day within 12 weeks. 3. For severe and life-threatening irAEs, IV corticosteroid should be initiated first followed by oral steroid. Other immunosuppressive treatment should be initiated if irAEs cannot be controlled by corticosteroids.				
Immune-related AEs	Toxicity grade or conditions (CTCAEv4.0)	Action taken to pembrolizumab	irAE management with corticosteroid and/or other therapies	Monitor and follow-up

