Pneumonitis	Grade 2	Withhold	
 
Administer corticosteroids (initial dose of 1-2 mg/kg prednisone or equivalent) followed by taper
 
	
 
Monitor subjects for signs and symptoms of pneumonitis
 
Evaluate subjects with suspected pneumonitis with radiographic imaging and initiate corticosteroid treatment
 
Add prophylactic antibiotics for opportunistic infections
 

	Grade 3 or 4, or recurrent Grade 2	Permanently discontinue		
Diarrhea / colitis	Grade 2 or 3	Withhold	
 
Administer corticosteroids (initial dose of 1-2 mg/kg prednisone or equivalent) followed by taper
 
	
 
Monitor subjects for signs and symptoms of enterocolitis (ie, diarrhea, abdominal pain, blood or mucus in stool with or without fever) and of bowel perforation (ie, peritoneal signs and ileus).
 
Subjects with Grade <math>\geq 2</math> diarrhea suspecting colitis should consider GI consultation and performing endoscopy to rule out colitis.
 
Subjects with diarrhea/colitis should be advised to drink liberal quantities of clear fluids. If sufficient oral fluid intake is not feasible, fluid and electrolytes should be substituted via IV infusion.
 

	Grade 4	Permanently discontinue		
AST / ALT elevation or Increased Bilirubin	Grade 2	Withhold	
 
Administer corticosteroids (initial dose of 0.5-1 mg/kg prednisone or equivalent) followed by taper
 
	
 
Monitor with liver function tests (consider weekly or more frequently until liver enzyme value returns to baseline or is stable
 

Immune-related AEs	Toxicity grade or conditions (CTCAEv4.0)	Action taken to pembrolizumab	irAE management with corticosteroid and/or other therapies	Monitor and follow-up
	Grade 3 or 4	Permanently discontinue	
 
Administer corticosteroids (initial dose of 1-2 mg/kg prednisone or equivalent) followed by taper
 
	

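### Table 4 omits the permanent stop for recurrent Grade 3 diarrhea that protocol Section 5.8.1 makes mandatory

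*Combined protocol and SAP*

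**What the plan says.** Section 5.8.1 introduces its list of stopping reasons with mandatory wording: "A subject must be discontinued from trial treatment but continue to be monitored in the trial for any of the following reasons". Two entries concern recurrence of a named toxicity: "Recurrent Grade 2 pneumonitis" and "Recurrent Grade 3 diarrhea". The section closes by making the stop irreversible: "Once a subject is discontinued, he/she shall not be allowed to restart treatment".

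Table 4 in Section 5.2.1.2.1 gives dose modification for immune-related events. Its pneumonitis row calls for permanent discontinuation at "Grade 3 or 4, or recurrent Grade 2". Its diarrhea/colitis row says to withhold at Grade 2 or 3 and to discontinue permanently at Grade 4, with no entry for a recurrent Grade 3 episode. General instruction 2 of the table says that, after withholding, "pembrolizumab can be resumed after AE has been reduced to Grade 1 or 0 and corticosteroid has been tapered". The row for all other immune-related events stops permanently at Grade 4 or recurrent Grade 3.

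The plan does not use the term trial treatment in one fixed way. The Trial Summary says that "each subject will be randomized to receive trial treatment (pembrolizumab + EP or placebo + EP"), and Table 2, headed Trial Treatments, lists carboplatin, cisplatin and etoposide beside pembrolizumab and saline. The note in Section 5.8.1 on the 35-cycle limit counts only the blinded agent: "Subjects who stop trial treatment after receiving 35 doses of pembrolizumab or saline placebo".

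**The concern.** Section 5.2.1.2 sends sites to Tables 3 through 7 for dose modifications, and neither the diarrhea/colitis row nor the general instructions of Table 4 point back to Section 5.8.1. A site managing a second Grade 3 episode from the table would find an instruction to withhold and a permission to resume, and nothing to say that the subject must come off treatment.

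The stake is subject safety and uniform conduct. Section 5.6.1 says the immune-related guidance applies when the investigator judges the event related to pembrolizumab, which is where re-exposure after a second severe episode matters most. Completed enrollment does not remove the issue, because pembrolizumab or placebo may be given for up to 35 cycles.

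A second, separate question is how far the 5.8.1 stop reaches. If it includes EP, sites also need to know how it fits with Table 7 footnote b, which lets chemotherapy go on at a modified dose when Grade 3 or higher diarrhea recurs.

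**Working it through.** No arithmetic applies. The check is to trace one case through each rule and then look for another rule that would close the gap.

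**Case.** A subject has a second Grade 3 diarrhea episode, judged related to pembrolizumab. It improves to Grade 1 or lower, with the steroid tapered, inside the 12-week limit in Table 4.

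- *Section 5.8.1:* recurrent Grade 3 diarrhea is on the mandatory list. Result: permanent stop.
- *Table 4, diarrhea/colitis row:* Grade 3 means withhold. Grade 4 was not reached, so the stop cell does not apply. General instruction 2 then permits resumption and sets no limit on the number of episodes. Result: withhold, then dosing may resume.

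**Is the difference deliberate?** The two recurrence stops stand together in 5.8.1. The pneumonitis one is carried into Table 4 and the diarrhea one is not. The catch-all row also has a recurrent Grade 3 stop. Table 4 as written is therefore more permissive for diarrhea/colitis than for immune-related events with no row of their own, and the text offers no reason for that.

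**Does another rule supply the stop?**

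- *Most conservative adjustment (Section 5.2.1.2).* This is worded for a subject with more than one toxicity and competing recommendations. Here there is one toxicity under two sections. The later sentence on basing changes on the event needing the greatest modification also chooses between events.
- *Limit on modifications (Section 5.2.1.2).* An agent is dropped at the third modification. Even if each hold counts as one, the second episode is only the second modification.
- *All-other row of Table 4.* Diarrhea/colitis has its own row, so the catch-all does not govern it.
- *12-week and steroid-dose limits (Table 4, general instruction 2).* These are met in this case by construction.

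None of the four clearly closes the gap.

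**Scope of the 5.8.1 entry.** Table 2 and the Trial Summary both count EP as trial treatment. The 35-dose note names only pembrolizumab or placebo, but EP ends at Cycle 4, so that note would name only the blinded agent on either reading. The balance of the text favors including EP. On that reading, a second Grade 3 episode stops EP as well, while Table 7 footnote b offers a dose modification. On the narrower reading, Section 5.2.1.2 lets chemotherapy continue alone in the first 4 cycles and there is nothing to reconcile. The plan does not say which is meant.

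**The case against.** The strongest reply is that this is an omission and not a clash of rules. Section 5.8.1 is mandatory. Table 4 is titled as guidelines and its resumption wording is permissive. A site can satisfy both by stopping, and harm requires a site to work from the table without regard to the discontinuation section. This reply stands in full and sets the severity. A reader might infer that the protocol gives sites two instructions that cannot both be obeyed; the text does not support that.

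Three other stronger readings are tempting and should be resisted.

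- *That EP may continue after a recurrence.* Table 2 and the Trial Summary point the other way, so writing in that permission could loosen a safety stop. The general causality rule in Section 7.2.4 does not settle the matter, because Section 5.2.1.2 has its own rule for dose modification and lets the investigator attribute a toxicity to a single agent.
- *That the excess exposure can be counted in cycles.* Suppose a first episode in Cycle 1 and a recurrence in Cycle 2, leaving 35 − 2 = 33 cycles. Table 4 directs steroids for Grade 2 or 3 diarrhea, tapered over at least 4 weeks before pembrolizumab resumes, and a cycle lasts 3 weeks, so the second dose could not be given on schedule. The third-modification limit and the investigator's freedom to stop also cut any such count.
- *That footnote b could never be used.* It covers Grade 3 and above, and other toxicities. On a literal reading of the 5.8.1 entry, a Grade 3 episode after a Grade 4 one could still fall under it.

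**Conclusion.** The point holds as a minor inconsistency. The dosing guide lacks a permanent stop that Section 5.8.1 requires, and no other dosing rule clearly supplies it. Anyone who reads both sections knows to stop; the exposure is limited to sites that dose from Table 4 alone.

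The size cannot be given as a number of subjects, because the documents state no rate of recurrent Grade 3 diarrhea. The two rules also cover different events: 5.8.1 takes in any recurrent Grade 3 diarrhea, Table 4 only what is judged related to pembrolizumab.

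There is no effect on the primary analyses, alpha or power. Efficacy is analyzed by intention to treat, and the primary PFS analysis dates progression regardless of study drug discontinuation. A reader might infer a distortion of PFS Sensitivity Analysis 2, which treats stopping as progression. That rule bears only on subjects with neither progression nor death, (453 − 387) / 453 = 14.6% of subjects at the planned event count, and within them only on any with recurrent Grade 3 diarrhea.

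On the reach of the 5.8.1 stop, the conclusion is narrower: the text leans toward including EP but does not settle it.

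**What to change.** 1. In the diarrhea/colitis row of Table 4, change the condition for permanent discontinuation from Grade 4 to Grade 4 or recurrent Grade 3. This matches Section 5.8.1 and follows the pattern of the pneumonitis and all-other rows.
2. Have the sponsor state in Section 5.8.1 whether the recurrent Grade 3 diarrhea stop also ends EP in Cycles 1 to 4, and reword Table 7 footnote b to agree. The review should ask for the decision and not presume that EP may go on.

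The cost is one table cell, a clarification of one list entry and one footnote, and a clarification letter to sites. Design, sample size and the primary analyses do not change.
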